APPENDIX E: RESPONSE CRITERIA FOR SOLID TUMORS

Evaluation of Target Lesions	
Complete Response (CR):	Disappearance of all target lesions
Partial Response (PR):	At least a 30% decrease in the sum of the LD of target lesions, taking as reference the baseline sum LD
Progressive Disease (PD):	At least a 20% increase in the sum of the LD of target lesions, taking as reference the smallest sum LD recorded since the treatment started or the appearance of one or more new lesions
Stable Disease (SD):	Neither sufficient shrinkage to qualify for PR nor sufficient increase to qualify for PD, taking as reference the smallest sum LD since the treatment started
Evaluation of Non-Target Lesions	
Complete Response (CR):	Disappearance of all non-target lesions and normalization of tumor marker level
Incomplete Response/ Stable Disease (SD):	Persistence of one or more non-target lesion(s) or/and maintenance of tumor marker level above the normal limits
Progressive Disease (PD):	Appearance of one or more new lesions and/or unequivocal progression of existing non-target lesions ¹

¹ Although a clear progression of “non target” lesions only is exceptional, in such circumstances, the opinion of the treating physician should prevail and the progression status should be confirmed later on by the review panel (or study chair).

Evaluation of Best Overall Response

The best overall response is the best response recorded from the start of the treatment until disease progression/recurrence (taking as reference for PD the smallest measurements recorded since the treatment started). In general, the subject's best response assignment will depend on the achievement of both measurement and confirmation criteria.

Target Lesions	Non-Target Lesions	New Lesions	Overall Response
CR	CR	No	CR
CR	Incomplete Response/SD	No	PR
PR	Non-PD	No	PR
SD	Non-PD	No	SD
PD	Any	Yes or No	PD
Any	PD	Yes or No	PD
Any	Any	Yes	PD

- Subjects with a global deterioration of health status requiring discontinuation of treatment without objective evidence of disease progression at that time should be classified as having “symptomatic deterioration.” Every effort should be made to document the objective progression even after discontinuation of treatment.
- In some circumstances it may be difficult to distinguish residual disease from normal tissue. When the evaluation of complete response depends on this determination, it is recommended that the residual lesion be investigated (fine needle aspirate/biopsy) to confirm the complete response status.

Source: Therasse P, Arbuck SG, Eisenhauer EA, Wanders J, Kaplan RS, Rubinstein L, et al. New guidelines to evaluate the response to treatment in solid tumors. European Organization for Research and Treatment of Cancer, National Cancer Institute of the United States, National Cancer Institute of Canada. *J Natl Cancer Inst* 2000;92:205–16.

APPENDIX F: SUMMARY OF CHANGES

PROTOCOL PX-171-010, AMENDMENT 3

Revisions have been made to the requirements for subjects with MM to undergo bone marrow aspirate and/or biopsy sample collection (for cytogenetic and fluorescent in situ hybridization [FISH] analysis): These procedures have been changed to optional at all time points, rather than required. An addition has been made to dose levels to accommodate subjects rolled over from previous studies. For clarity, updates to AE recording (in the event of a toxicity leading to a dose reduction or discontinuation), and AE reporting following the last dose of study, have also been made in this document.

Administrative updates, editorial changes, and style and formatting revisions have been made to improve clarity and consistency throughout the document. Specific changes are described in the table below. Changes noted in specific sections were also made in the protocol summary and elsewhere in the document, as applicable. Revised text is presented in bold format.

Section No.	Amendment 2	Amendment 3	Rationale
Synopsis: PROCEDURES Efficacy Measures	For subjects with multiple myeloma (MM) entering the extended study with a partial response (PR), minimal response (MR), or stable disease (SD); bone marrow biopsies for cytogenetic and fluorescence in situ hybridization (FISH) evaluation will be required at screening. A bone marrow biopsy in these subjects will also be required at end of study for cytogenetic and FISH evaluation if the reason for study discontinuation is disease progression.	For subjects with multiple myeloma (MM) entering the extended study with a partial response (PR), minimal response (MR), or stable disease (SD); bone marrow biopsies for cytogenetic and fluorescence in situ hybridization (FISH) evaluation will be optional at screening. A bone marrow biopsy in these subjects will also be optional at end of study for cytogenetic and FISH evaluation if the reason for study discontinuation is disease progression.	Revision. To allow bone marrow biopsies for cytogenetic and fluorescence in situ hybridization (FISH) to be optional, rather than required. To accommodate subjects where bone marrow biopsies are unfeasible or unsafe to obtain.
Synopsis: PROCEDURES Efficacy Measures	For subjects with MM entering the extended study with stringent complete response (sCR), complete response (CR), or very good partial response (VGPR), a bone marrow biopsy for cytogenetic and FISH analyses will only be required upon the establishment of disease progression.	For subjects with MM entering the extended study with stringent complete response (sCR), complete response (CR), or very good partial response (VGPR), a bone marrow biopsy for cytogenetic and FISH analyses will also be optional upon the establishment of disease progression.	Revision. To allow bone marrow biopsies for cytogenetic and fluorescence in situ hybridization (FISH) to be optional, rather than required, upon the establishment of disease progression for subjects with MM. To accommodate subjects where bone marrow biopsies are unfeasible or unsafe to obtain.
Section 6.2.1 Dose Frequency and Dose Level Reductions	Carfilzomib Dose Levels 11 mg/m ² 15 mg/m ² 20 mg/m ² 27 mg/m ² 36 mg/m ² * 45 mg/m ² * * Dose level for 30-minute infusion	Carfilzomib Dose Levels 11 mg/m ² 15 mg/m ² 20 mg/m ² 27 mg/m ² 36 mg/m ² * 45 mg/m ² * 56 mg/m²* * Dose level for 30-minute infusion	Addition. A dose level is added since subjects can escalate up to 56 mg/m ² based on dose levels administered in PX-171-007.
Section 6.4.1 Required Concomitant Medication	A proton-pump inhibitor will be used orally daily to prevent peptic disease.	Deleted	Revision. Proton-pump inhibitors are not a required concomitant medication.

Section No.	Amendment 2	Amendment 3	Rationale
Section 7 Study Tests and Observations	These data will not be routinely collected .	These data will not be routinely recorded on CRFs .	Clarification. These data may be collected, but will not be routinely recorded on CRFs.
Section 7.1 Screening (Days -30 to -1)	Bone marrow aspirate and/or biopsy sample collection for cytogenetic and fluorescent in situ hybridization (FISH) analysis (only for MM subjects whose disease status at study entry is PR, MR or SD).	OPTIONAL: Bone marrow aspirate and/or biopsy sample collection for cytogenetic and fluorescent in situ hybridization (FISH) analysis (only for MM subjects whose disease status at study entry is PR, MR or SD).	Revision. To allow bone marrow biopsies for cytogenetic and fluorescence in situ hybridization (FISH) to be optional at Screening, rather than required, for MM subjects whose disease status at study entry is PR, MR or SD. To accommodate subjects where bone marrow biopsies are unfeasible or unsafe to obtain.
Section 7.1 Screening (Days -30 to -1) Section 7.2 Cycle 1 (Day 1) Section 7.3 Cycle 1 (Days 2, 8, 9, 15, and 16) Section 7.4 Cycles 2 and Higher (Day 1) Section 7.5 Cycles 2 and Higher (Days 2, 8, 9, 15, and 16) Section 7.6 Cycles 3 and Every 3 Cycles (Day 1) Section 7.7 End of Study Assessments	Record Grade 3 and 4 AEs, including SAEs	Record Grade 3 and 4 AEs, and all SAEs	Clarification. All SAEs are to be recorded.

Section No.	Amendment 2	Amendment 3	Rationale
Section 7.2 Cycle 1 (Day 1) Section 7.3 Cycle 1 (Days 2, 8, 9, 15, and 16) Section 7.4 Cycles 2 and Higher (Day 1) Section 7.5 Cycles 2 and Higher (Days 2, 8, 9, 15, and 16) Section 7.6 Cycles 3 and Every 3 Cycles (Day 1)	Record AE (any Grade) leading to a missed carfilzomib dose, carfilzomib dose reduction, or discontinuation.	Record AE (any Grade) leading to a missed carfilzomib dose, carfilzomib dose reduction, or discontinuation. In the event of a toxicity leading to a dose reduction or discontinuation, pertinent laboratory measurements and concomitant medications will be collected and monitored as unscheduled visits.	Addition. To include information/instructions regarding collection of laboratory measurements and concomitant medications in the event of toxicity leading to dose reduction or discontinuation.
Section 7.7 End of Study Assessments Section 8 Study Discontinuation	Bone marrow aspirate and/or biopsy for cytogenetic and FISH analysis (only required for MM subjects whose reason for study discontinuation is PD).	OPTIONAL: Bone marrow aspirate and/or biopsy for cytogenetic and FISH analysis (only required for MM subjects whose reason for study discontinuation is PD).	Revision. To allow bone marrow biopsies for cytogenetic and fluorescence in situ hybridization (FISH) to be optional, rather than required, for MM subjects whose reason for study discontinuation is PD. To accommodate subjects where bone marrow biopsies are unfeasible or unsafe to obtain.
Section 7.9.1 Cytogenetic and FISH Studies Appendix A Footnote	A bone marrow biopsy and/or aspirate for determining percent plasma cell involvement, including metaphase cytogenetic and FISH studies, are mandatory for all MM entering with a PR, MR, or SD. Samples for cytogenetic and FISH analysis will also be required for all MM subjects who discontinue study due to PD.	A bone marrow biopsy and/or aspirate for determining percent plasma cell involvement, including metaphase cytogenetic and FISH studies are optional for all MM subjects entering with a PR, MR, or SD. Samples for cytogenetic and FISH analysis will also be optional for all MM subjects who discontinue study due to PD.	Revision. To allow bone marrow biopsies for cytogenetic and fluorescence in situ hybridization (FISH) to be optional, rather than required, for MM subjects entering with a PR, MR, or SD and for MM subjects who discontinue study due to PD. To accommodate subjects where bone marrow biopsies are unfeasible or unsafe to obtain.

Section No.	Amendment 2	Amendment 3	Rationale
Section 9.3 Adverse Events Reporting Procedures	AEs will be collected from the time the subject signs informed consent through 30 days following the last dose of study drugs.	AEs will be collected from the time the subject signs informed consent through 30 days following the last dose of study drugs, or initiation of a new anti-cancer therapy.	Addition. To include information/instruction regarding collection of AEs. AEs should not continue to be recorded /collected if a subject initiates a new anti-cancer therapy.

1 INTRODUCTION

This Statistical Analysis Plan (SAP) covers a number of sections that describe how the data from the trial is going to be analyzed to assess the clinical safety and efficacy associated with the treatment under consideration.

This SAP was prepared in accordance with Protocol Amendment 3, dated March 25, 2011. Any changes that are made to the planned analyses after the SAP is finalized, along with an explanation as to when and why they occurred, will be noted in any Clinical Study Report (CSR) produced for the study. Any changes made to the planned analyses that are in the protocol will be identified and documented in this document.

2 STUDY OVERVIEW

2.1 Study Design

This is a multicenter, open-label, Phase 2 study of carfilzomib to monitor the safety and efficacy of long-term or continuing carfilzomib therapy for subjects who previously completed a primary carfilzomib treatment study. Only subjects who have completed a prior carfilzomib treatment study will be eligible for the current study.

2.2 Study Objective

To evaluate the safety and efficacy of long-term or continuing carfilzomib treatment in subjects who have completed a previous carfilzomib treatment study.

2.3 Sample Size Considerations

The total number of subjects to be enrolled in the study is dependent upon the number of subjects who have completed the primary carfilzomib treatment protocols. It is anticipated that approximately 100 subjects will be enrolled in this study. Formal power calculation was not used to determine the sample size.

3 ANALYSIS ENDPOINTS

3.1 Primary Endpoints - Safety

- Reported peripheral neuropathy AEs (All Grades)
- Reported Grades 3 and 4 AEs
- SAEs
- Grade 1 through Grade 4 AEs leading to a missed carfilzomib dose or a carfilzomib dose reduction, or discontinuation

3.2 Secondary Endpoints - Efficacy

- Overall Survival (OS)
- Progression Free Survival (PFS)
- Time to Progression (TTP)

Tumor measurements and efficacy assessments will be in accordance with the methods employed in the subject's prior carfilzomib study. For subjects participating in a carfilzomib trial without prior tumor measurements and efficacy assessments (eg, PX-171-008), tumor assessments will be conducted at the time of screening for the current study using the appropriate method (eg, RECIST criteria for solid tumors); these assessments will be used as the subjects' baseline disease assessments for determining response and progression while on the current protocol, PX-171-010.

4 ANALYSIS POPULATIONS

The analysis and reporting of the data from this study will be performed using the following populations.

4.1 Safety Population

The Safety population consists of all enrolled subjects who received at least 1 dose of carfilzomib after enrollment in PX-171-010.

4.2 Full Analysis Set Population

The Full Analysis Set (FAS) population will serve as the primary population for the analysis of the disease response data. The FAS population is a subset of all enrolled subjects, with subjects excluded for the following reasons:

- No post-baseline endpoint data subsequent to at least 1 dose of study treatment on the PX-171-010 protocol (applicable only to PX-171-008 subjects).
- Lack of baseline data for those analyses that require baseline data

5 ANALYTIC DEFINITIONS

5.1 Study Day 1

Study Day 1 corresponds to the date of the first dose of carfilzomib in this study. For subjects who receive at least one dose of carfilzomib, the earliest dosing date recorded on the Study Drug Administration case report form (CRF) will be used to determine Study Day 1.

5.2 Study Day

Study Day represents the elapsed number of days from Study Day 1, inclusive. Unless otherwise specified, the timing of all study-related events, assessments, and interventions will be calculated relative to Study Day 1. If assessment date is after date of study day 1, study day will be calculated as:

$$\text{Study Day } n = (\text{Date of assessment} - \text{Date of Study Day 1}) + 1 \text{ day}$$

If assessment date is before date of study day 1, study day will be calculated as:

$$\text{Study Day } -n = \text{Date of assessment} - \text{Date of Study Day 1}$$

5.3 Cycle 1 / Cycle Day 1

The first 28-day treatment cycle will begin with the first dose of carfilzomib, and will be denoted as “Cycle 1 / Cycle Day 1”. In general, the start date of each cycle (i.e., Cycle Day 1 of Cycle k , where $k=1$ to last cycle) equals the date of the first dose of carfilzomib administered in the corresponding cycle. If carfilzomib is permanently discontinued,

then the cycle and cycle day for study-related assessments done after the last cycle of carfilzomib will be replaced in the tables, figures, and listings with the visit label (e.g., end of study assessment). The visit date and study day also will be used to identify the timing of such assessments.

5.4 Cycle k / Cycle Day j

Cycle Day j represents the elapsed number of days since the first dose of carfilzomib in Cycle k.

$$\text{Cycle Day j} = (\text{Date of assessment} - \text{Date of Day 1 in Cycle k}) + 1 \text{ day}$$

Unless otherwise specified, the timing of study-related visits and assessments will be calculated relative to Cycle Day 1 in each cycle.

As noted previously, if carfilzomib is permanently discontinued, then the cycle and cycle day for study-related assessments done after the last cycle of carfilzomib will be replaced in the tables, figures, and listings with the visit name (e.g., End of Study assessment).

The visit date and study day also will be used to identify the timing of such assessments.

5.5 Baseline

If subjects had not received other anti-cancer therapies and not reached progressive disease when they enrolled in study 010, baseline disease assessments from the initial study will be used for baseline values for determining response and progression unless no prior assessments were collected (eg, PX-171-008). For those subjects who didn't have baseline collected in prior study, tumor assessments will be conducted at the time of screening for the current study using the appropriate method. And for those who received other anti-cancer therapies and/or progressive disease when they enrolled in study 010, baseline values from current study will be used.

During the study, the addition of certain approved agents with known antitumor activity or increase of carfilzomib dose and/or frequency is permitted if there is concern for disease progression and per Investigator discretion in consultation with the Onyx Medical Monitor. If it happens, measurements at the time of addition of new agents will be used as new baseline.

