7.7.2 Progression Free Survival (PFS)

PFS is defined as number of days between start of treatment and first evidence of documented disease progression or death (due to any cause), whichever occurs first. Disease progression will be determined by the local investigator for regimens with the same baseline using the International Uniform Response Criteria ([Durie et al. 2006, with corrections](#)) (IMWG-URC) for multiple myeloma subjects and RECIST criteria ([Therasse et al. 2000](#)) for solid tumor subjects. PFS will be re-calculated whenever the baseline is reset due to addition of new anti-cancer therapy or increase of carfilzomib dose/frequency:

- 1) For regimens that continue from initial study without baseline being reset, if subjects didn't progress before PX-171-010, then PFS for the period from initial study to PX-171-010 study will be calculated as Disease Progression /Death Date – Date of first dose in initial study + 1 day, and PFS for the period of PX-171-010 study only will be calculated as Disease Progression /Death Date – Date of first dose in PX-171-010 + 1 day.
- 2) For regimens that start in PX-171-010 study with baseline being reset from initial study or previous regimens, PFS will be calculated as Disease Progression /Death Date –

Date of first dose in the first regimen among the regimens with common baseline + 1 day.

PFS will be right-censored for subjects who met one of the following conditions: 1) no baseline disease assessments or any post-baseline assessments, 2) alive and does not have documentation of disease progression before a data analysis cutoff date. The PFS censoring rules are described in Table 1.

Table 1. Censoring Rules for PFS Analysis

Situation	Date of Progression or Censoring	Outcome
No baseline disease assessments or any post-baseline assessments	Date of first dose	Censored
Alive and without documentation of disease progression	Date of last disease assessment	Censored
Death or disease progression between planned disease assessments	Date of death or first disease assessment showing disease progression, whichever occurs first	Progressed
Death or PD immediately after more than 1 consecutively missed disease assessment visit*	Date of last disease assessment before the first missed visit	Censored
Death before first disease assessment	Date of death	Progressed

* If death or PD is more than 168 days after previous disease assessment, or the first dosing date if there is no previous disease assessment.

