The number and percentage of subjects with events, the number and percentage of subjects censored will be calculated for each disease cohort (MM, solid tumor) by regimen. The denominator for each regimen will be subjects who had the regimen.

Kaplan-Meier method will be used to estimate the distribution of PFS. The 25%, 50% and 75% KM quartiles will be provided along with a two-sided 95% confidence interval ([Klein and Moeschberger, 1997](#)).

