7.7.3 Time to Progression (TTP)

TTP is defined as number of days between start of treatment to the first documentation of disease progression. TTP will be re-calculated whenever the baseline is reset due to addition of new anti-cancer therapy or increase of carfilzomib dose/frequency:

- 1) For regimens that continue from initial study without baseline being reset, if subjects didn't progress before PX-171-010, then TTP for the period from initial study to PX-171-010 study will be calculated as Date of Disease Progression – Date of first dose in initial study + 1 day, and TTP for the period of PX-171-010 study only will be calculated as Date of Disease Progression – Date of first dose in PX-171-010 + 1 day.
- 2) For regimens that start in PX-171-010 study with baseline being reset from initial study or previous regimens, TTP will be calculated as Date of Disease Progression – Date of first dose in the first regimen among the regimens with common baseline + 1 day. The same censoring rules, except for death, as in analysis of PFS ([Section 7.7.2](#)) will be applied in calculation of TTP. Subjects who die before disease progression will be censored at death date.

The number and percentage of subjects with events, the number and percentage of subjects censored will be calculated. Kaplan-Meier method will be used to estimate the distribution of TTP for each disease cohort by regimens. The 25%, 50% and 75% KM quartiles will be provided along with a two-sided 95% confidence interval ([Klein and Moeschberger, 1997](#)).

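### When SAP 5.5 resets the baseline on suspicion of progression, SAP Table 1 as written censors the earlier regimen at its last assessment, which biases that regimen's PFS and TTP upward; the reset needs its own row and a sensitivity analysis.

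*SAP*

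**What the plan says.** **Trigger.** Besides added agents, SAP 5.5 names a second kind of change: "increase of carfilzomib dose and/or frequency is permitted if there is concern for disease progression and per Investigator discretion". Documented progression is not required. Protocol 6.4.2 uses the same trigger for added agents.

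**Reset.** SAP 5.5 then says: "If it happens, measurements at the time of addition of new agents will be used as new baseline".

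**Restart.** SAP 7.7.2: "PFS will be re-calculated whenever the baseline is reset due to addition of new anti-cancer therapy or increase of carfilzomib dose/frequency". SAP 7.7.3: "TTP will be re-calculated whenever the baseline is reset due to addition of new anti-cancer therapy or increase of carfilzomib dose/frequency". Both sections give the start date for the regimen after the reset. Neither says how the regimen before it ends.

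**Reporting by regimen.** For PFS, "The denominator for each regimen will be subjects who had the regimen". For TTP, "Kaplan-Meier method will be used to estimate the distribution of TTP for each disease cohort by regimens".

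**Censoring.** Table 1 in SAP 7.7.2 has five rows: no baseline or post-baseline assessment; "Alive and without documentation of disease progression", which is censored at the last disease assessment; death or progression between planned assessments; death or progression after more than one missed assessment; and death before the first assessment. None mentions a regimen change, a new therapy or a reset. TTP takes over "The same censoring rules, except for death, as in analysis of PFS". Protocol 10.4.2 gives a censoring date only for subjects who end the study without documented progression.

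**The concern.** Kaplan-Meier estimation assumes that a censored subject has the same outlook as those still at risk. A subject whose regimen is intensified because the investigator suspects failure does not. If such subjects are censored at the change, likely failures leave the risk set just before they would count, and the earlier regimen looks better than it was.

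PFS and TTP are two of the three secondary endpoints. SAP 7.7.1 plans no Kaplan-Meier estimate for OS, so they supply the only time-to-event curves in the plan, with quartiles and 95% confidence intervals. At stake is how those by-regimen figures are read. No hypothesis test is involved.

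**Working it through.** The plan gives no PFS figure and no switching rate, so there is no stated number to reproduce. The check has two parts.

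**1. Which rule applies to a reset without documented progression?**
- The second Table 1 row fits: the subject is alive, has no documented progression, and is censored at the last assessment.
- SAP 7.7.2 judges progression among regimens that share a baseline. Later progression, measured from the new baseline, then belongs to the later regimen. This supports the same reading.
- The matching condition in the text of 7.7.2 is worded by status at the data cutoff. A carry-through reading, in which later progression or death counts for the earlier regimen, is therefore less natural but not excluded.

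**2. How large could the bias be?** (illustration only)

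Inputs:
- Visits every 84 days: the protocol's schedule is every 3 cycles of 28 days, and the 168 days in the Table 1 footnote is two such intervals.
- Assumed: constant hazard, true median 300 days, progression dated at the visit, and no switch before the first visit.
- Share switched, *s*: the proportion of subjects free of progression at visit 1 who are ever switched. This is assumed and varied.

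Formulas:
- Hazard per interval: h = 1 − exp(−ln 2 × 84/300) = 0.1764. True PFS at day 336 (visit 4) = 0.8236⁴ = 0.46.
- At each visit, p is the chance of a switch if progression would be found at the next visit, and q is the chance otherwise. The hazard seen at visits 2 to 4 is h′ = (1−p)h / [(1−p)h + (1−q)(1−h)], and S(336) = (1−h)(1−h′)³.
- Every switch one visit before progression: q = 0 and s = p. At s = 0.30, h′ = 0.1304 and S = 0.8236 × 0.8696³ = 0.54.
- Half the switches false alarms: q = ph/(1−h). Then s = 2p/(1+p), so p = s/(2−s). At s = 0.30, p = 0.1765, q = 0.0378, h′ = 0.1549 and S = 0.8236 × 0.8451³ = 0.50.
- Switch counted as an event: with w = ph + q(1−h), S = (1−h)(1−w)[(1−h′)(1−w)]³. At s = 0.30 with q = 0, w = 0.0529 and S = 0.44. With half false alarms, w = 0.0623 and S = 0.38.

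PFS at day 336 (true value 0.46):

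| Share switched | 10% | 20% | 30% | 50% |
|---|---|---|---|---|
| Censored, all switches precede progression | 0.49 | 0.51 | 0.54 | 0.61 |
| Censored, half false alarms | 0.47 | 0.48 | 0.50 | 0.54 |
| Event, all switches precede progression | 0.45 | 0.44 | 0.44 | 0.42 |
| Event, half false alarms | 0.44 | 0.41 | 0.38 | 0.33 |

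Simulation with 400,000 subjects per setting agrees with all four rows to within about 0.002. In the first row the observed median, which moves in 84-day steps, is 336 days with no switching or 10%, 420 days at 20 to 30%, and 504 days at 50%. With the first row's assumptions and no switching, then 10, 20, 30 and 50% switched, an assumed median of 200 days gives 0.31, 0.34, 0.36, 0.40 and 0.47, and 400 days gives 0.56, 0.58, 0.61, 0.63 and 0.69.

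For scale, the 95% half-width around 0.46, ignoring censoring, is 1.96 × √(0.46 × 0.54/n). That is 0.10 for n = 100 (the planned total over both cohorts) and 0.14 for n = 50.

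**The case against.** **A rule already exists.** A reader might infer that the SAP leaves the earlier regimen with no outcome at all. That goes too far: the second Table 1 row and the common-baseline wording together give a usable outcome and date. What stands is that this outcome follows from a row not written for a reset, that it censors on suspected failure, and that carry-through is not ruled out.

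**The scope is narrow.** A reader might infer that every dose increase is affected. Progression documented before the change is already a Table 1 event. Protocol 1.5 ties dose escalation to subjects whose disease progresses, while protocol 6.2.7 states no such condition; those passages should be reconciled. Added agents under protocol 6.4.2 are the clearest route that needs only suspicion.

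**Toxicity re-escalation.** A reader might infer that returning to a higher dose after a toxicity reduction also resets the baseline. SAP 5.5 conditions the change on suspected progression, so the text does not support this.

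**The effect is small against the noise.** Up to about 30% switched, the largest shift at the 300-day median is 0.54 − 0.46 = 0.08, inside the half-widths of 0.10 and 0.14. False alarms roughly halve it. This stands and limits the weight of the point. Bias does not shrink with sample size, however, and the direction is upward in every censored scenario above.

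**Conclusion.** The point holds at minor to moderate weight. As written, the plan censors the earlier regimen at a reset prompted by suspected progression, and this biases that regimen's PFS and TTP upward. With the assumed 300-day median, the shift in PFS at day 336 is 0.03 to 0.08 for 10 to 30% switched if every switch anticipates progression, and 0.01 to 0.04 if half are false alarms. At 50% it is 0.15 and 0.08 respectively. The sizes rest on an assumed median, hazard, visit timing and share switched; the direction rests only on switched subjects being at higher risk than those who stay.

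A reader might infer that the trial's main conclusion is at risk. The documents do not support that: the primary endpoint is safety, protocol 10.1 states that no prespecified hypothesis is tested, and the sample size has no power basis.

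**What to change.** 1. Add a Table 1 row for a baseline reset without documented progression: the earlier regimen is censored at the last disease assessment on or before the change, and the number so censored is reported by regimen. Carry the row into 7.7.3.
2. Add a sensitivity analysis of PFS and TTP that counts a change made for suspected progression as an event on the date of change. Label it conservative. First confirm that the reason on the regimen-change CRF identifies this category; SAP 7.4 shows only that reasons are collected.
3. Word the reset in 5.5 to cover dose or frequency increases made for suspected progression, as 7.7.2 and 7.7.3 do. At present 5.5 fixes the new measurement only at the addition of agents.

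A single PFS per subject that ignores resets is tempting, but the investigator judges progression within a common baseline, so such a curve would mix two references. It should not be added unless the reference after a reset is specified.

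The cost is one table row, a few sentences and a little programming. No new data are needed if the CRF reason is specific enough. The downside is a sensitivity result that is pessimistic when switches are false alarms, as the last table row shows. All three changes concern endpoint derivation and leave treatment decisions alone.
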